Physical ExaminationXXXXXXXXXVital SignsXXXXXXXXXPregnancy test 1XXXXXXXXClinical Laboratory assessments 2XXXXXXXEligibility confirmationIXXXXXXXCRP 3XXXXXXXXXWhole blood count and differential count 4XXXXXXXProCalcitonin (PCT) 3XXXXXXXOxygen requirement (oxygen flow or oxygenation index)XXXXXXLength of ICU stay (hours)XXXXXXXLength of time on mechanical ventilation (days)XXXXXXLength of time on mechanical ventilation (days)XXXXXXX	Informed Consent	Х						
Vital Signs X X X X X X X X X X X X X X X X X X X X X X X X X X X X X X X X X X X X X X X X X X X X X X X X X X X X X X X X X X X X X X X X X X X X X X X X X X X X X X X X X X X X X X X X X X X X X X X X X X X X X X X X X <th< td="">Medical History	Х							</th<>	Medical History	Х						
Pregnancy test 1XIIIIIIClinical Laboratory assessments 2XXXXXXXXXEligibility confirmation 2XXXXXXXXXCRP 3XXXXXXXXXXWhole blood count and differential count 4XXXXXXXXProCalcitonin (PCT) 3XXXXXXXXXOxygen requirement (oxygen flow or oxygenation index)XXXXXXXLength of ICU stay (hours)IXXXXXXXXLength of time on mechanical ventilation (days)XXXXXXXX	Physical Examination	х	х	х	х	х	х	х
Clinical Laboratory assessments 2XXXXXXXXEligibility confirmationXXXXXXXXCRP ³ XXXXXXXXXWhole blood count and differential count ⁴ XXXXXXXProCalcitonin (PCT) ³ XXXXXXXXD-Dimer ³ XXXXXXXXOxygen requirement (oxygen flow or oxygenation index)XXXXXXXLength of ICU stay (hours)XXXXXXXXXLength of time on mechanical ventilation (days)XXXXXXXXLength of time on mechanical ventilation (days)XXXXXXX	Vital Signs	Х	Х	Х	Х	Х	Х	Х
2XXXXXXXXXXEligibility confirmationXXXXXXXXXCRP³XXXXXXXXXXWhole blood count and differential count 4XXXXXXXXProCalcitonin (PCT)³XXXXXXXXXD-Dimer³XXXXXXXXXOxygen requirement (oxygen flow or oxygenation index)XXXXXXXLength of ICU stay (hours)XXXXXXXXLength of stay in the hospital (days)XXXXXXXXLength of time on mechanical ventilation (days)XXXXXXXX	Pregnancy test ¹	Х						Х
CRP 3XXXXXXXXXXXXXXXXXXXXXXXXXXXXXXXXXXXXXXXXXXXXXXXXXXXXXXXXXXXXXXXXXXXXXXXXXXXXXXXXXXXXXXXXXXXXXXXXXXXXXXXXXXXXXXXXXXXXXXXXXXXXXXXXXXXXXXXXXXXXXXXXXXXXXXXXXXXXXXXXXXXXXXXXXXXXXXXXXXXXXXXXXXXXXXXXXXXXXXXXXX		х	х	х	х	х	х	Х
Whole blood count and differential count 4XXXXXXXXXProCalcitonin (PCT) 3XXXXXXXXXD-Dimer 3XXXXXXXXXOxygen requirement (oxygen flow or oxygenation index)XXXXXXXLength of ICU stay (hours)XXXXXXXXLength of stay in the hospital (days)XXXXXXXLength of time on mechanical ventilation (days)XXXXXXX	Eligibility confirmation		х					
differential count 4XXXXXXXXXXXXXXXXXXXXXXXXXXXXXXXXXXXXXXXXXXXXXXXXXXXXXXXXXXXXXXXXXXXXXXXXXXXXXXXXXXXXXXXXXXXXXXXXXXXXXXXXXXXXXXXXXXXXXXXXXXXXXXXXXXXXXXXXXXXXXXXXXXXXXXXXXXXXXXXXXXXXXXXXXXXXXXXXXXXXXXXXXXXXXXXXXXXXXXXXX	CRP ³	Х	Х	Х	Х	Х	Х	Х
D-Dimer 3XXXXXXXXXOxygen requirement (oxygen flow or oxygenation index)XXXXXXXXLength of ICU stay (hours)XXXXXXXXLength of stay in the hospital (days)XXXXXXXLength of time on mechanical ventilation (days)XXXXXX		x	x	х	х	x	Х	х
D-Dimer 3XXXXXXXXXOxygen requirement (oxygen flow or oxygenation index)XXXXXXXXLength of ICU stay (hours)XXXXXXXXLength of stay in the hospital (days)XXXXXXXLength of time on mechanical ventilation (days)XXXXXX	ProCalcitonin (PCT) ³	Х	Х	Х	Х	Х	Х	х
flow or oxygenation index)XXXXXXXXXXXXXXXXXXXXXXXXXXXXXXXXXXXXXXXXXXXXXXXXXXXXXXXXXXXXXXXXXXXXXXXXXXXXXXXXXXXXXXXXXXXXXXXXXXXXXXXXXXXXXXXXXXXXXXXXXXXXXXXXXXXXXXXXXXXXXXXXXXXXXXXXXXXXXXXXXXXXXXXXXXXXXXXXXXXXXXXXXXXXXXXXXXXXXXXX 	Х	Х	Х	Х	Х	Х	Х	Х	Х	Х	Х	Х	Х	Х
Length of stay in the hospital (days)XXXXXXXLength of time on mechanical ventilation (days)XXXXXXX		x	х	х	х	x	х	х
(days)XXXXXXLength of time on mechanical ventilation (days)XXXXXX	Length of ICU stay (hours)		х	х	х	х	х	Х
ventilation (days)			х	х	х	х	х	х
Survival (days) X X X X X X X	-		x	x	x	x	х	х
	Survival (days)		Х	Х	Х	Х	Х	Х

Ventilator-Associated Pneumonia (VAP) or hospital acquired pneumonia		x	x	x	x	х	x
Acute physiology score + age points + chronic health points (APACHE score)		x	x	х	x	х	х
Ordinal score (WHO scoring tool)		х	х	х	х	х	х
Blood draw for pharmacodynamics (PD) ⁵	х	х	х	х	х	х	x
Blood draw for biomarkers ⁶	х	х	х	х	х	х	Х
Bronchial secretion for PD and biomarkers ^{5,6, 7}		х	x	х	x	х	x
nebulised dornase alfa administration ⁸		х	x	х	x	х	
Adverse Events review ¹²		х	х	х	х	х	х
Concomitant Medication review	х	х	х	х	х	х	х
Questions about breathing ⁹							Х

- 1. A urine pregnancy test
- Clinical Laboratory assessments include: glutamate pyruvate transaminase (GPT / ALAT), glutamicoxaloacetic transaminase (GOT / ASAT), gamma-glutamyl transferase (gamma-GT), alkaline phosphatase, total bilirubin, creatinine, chloride, potassium, sodium, total protein, albumin, Lactate, Renal function: (Creatinine, Urea and Na, K, Cl), Clotting screen including Prothrombin time, Bone profile (ca2+), High-sensitivity troponin, Ferritin, LDH, Creatinine
- 3. CRP, PCT and D-Dimer are measured in the clinical laboratory sample
- Full Blood Count: leukocytes, erythrocytes, haemoglobin, haematocrit, mean corpuscular volume (MCV), mean corpuscular haemoglobin (MCH), platelets, neutrophils, eosinophils, basophils, lymphocytes, monocytes
- 5. Pharmacodynamics: may include but is not limited to Cell-free DNA (cfDNA), Circulating histone, Citrullinated H3, NET Elisa assay
- Biomarkers: may include but is not limited to Circulating pro-inflammatory cytokines (e.g. IL-6, TNFα, IL-1β, IL-8), Markers of activation of the coagulation (e.g. fibrin, tissue factor, Von Willebrand factor,

thrombin, thromboxane A2) and complement cascade (e.g. C1q), haemolysis (e.g. red blood cell lysis), NET formation

- 7. Bronchial secretions will be collected as appropriate for clinical reasons only (e.g. spontaneous expectorant or bronchoscopy during MV)
- 8. Dornase alfa administered daily at 2.5mg BID by nebuliser
- 9. In participants who are discharged prior to Day35, a follow-up telephone call will take place to ask about their breathing.
- 10. In participants who receive dornase alfa (2.5mg BID) beyond Day7, additional blood draws and procedures will take place on Day9, Day11, Day14
- 11. Final study visit is at discharge or Day35 whichever comes first
- 12. Adverse events will be recorded every day and not just on study visit days

# **Exploristics Limited**

# Identifier: EXP20012

Clinical Study Identifier: 132333

Copyright 2021 Exploristics Limited. All rights reserved. Unauthorised copying or use of this information is prohibited.

Audit Trail For This Document				
Compiled by/Affiliation	Type of Change	Date	Version	
[name], Exploristics	Creation	29OCT2020	1.0	
[name], Exploristics	Edits following discussions with the client.	06NOV2020	1.1	
[name], Exploristics	Accepted client re- wording and changed the maximum permitted number of individuals to 48 (not 52).	16DEC2020	1.2	
[name], Exploristics	Changed from propensity score matching at the interm to inclusion of all eligible historical controls. Included mock interim tables. Changed "number of comorbidities" in the adjustment and matching analysis to "any key comorbities".	04JAN2021	1.3	
[name], Exploristics	Updated to expand the details of the primary and secondary analyses in preparation for the final analysis	29JAN2021	1.4	
[name], Exploristics	Updated the mechanical ventilation and ventilator- associated pneumonia analysis, as incidence cannot be reliably inferred from the data. Clarified how "time on oxygen" will be calculated. Clarified which covariates will be removed from models if convergence fails or over- fitting present.	14JUL2021	1.5	
[name], Exploristics	Removed oxygen use summary by day as data available in COVASE and HC participants not sufficient for the analysis to be performed. Removed HCs from the	12AUG2021	1.6	

# **Exploristics Limited**

# Identifier: EXP20012 Clinical Study Identifier: 132333

	WHO ordinal scale analysis, as not available in HCs.	· · .	· · · · ·
Effective Date		12AUG2021	1.6

13. ATTACHMENTS	
13.1 Table of Contents for Data Display Specifications	

# **Exploristics Limited**

# CONFIDENTIAL

# ABBREVIATIONS

# Identifier: EXP20012 Clinical Study Identifier: 132333

AE	Adverse Event
APACHE	Acute physiology score + age points + chronic health points
BAC	Best Available Care
BID	Twice per day
CF	Cystic Fibrosis
cfDNA	Cell-free DNA
CI	Chief Investigator
CoV	Coronavirus
CRF	Case Report Form -
CRP	C-reactive protein
DNA	Deoxyribonucleic acid
DNase	Deoxyribonuclease
EudraCT	European Clinical Trials Database
FDA	Federal drug administration
FVC	Forced vital capacity
НЗ	Histone 3
ICU	Intensive care unit
ΙL-1 β	Interleukin -1 beta
IL-6	Interleukin-6
IL-8	Interleukin-8
ISARIC	International Severe Acute Respiratory and Emerging Infection
	Consortium
MPO	Myeloperoxidase
MV	Mechanical Ventilation
NIHR	National Institute for health research
NETs	Neutrophil extracellular traps
PCR	Polymerase chain reaction
PCT	ProCalcitonin
PD	Pharmacodynamics
QD	Once per day
RECOVERY	Randomised evaluation of COVID-19 therapy
RCT	Randomised Controlled Trial
SAP	Statistical Analysis Plan
SAE	Serious Adverse Event
SOFA	Sepsis-related Organ Failure Assessment
SOP	Standard Operating Procedure
ΤΝΓα	Tumour necrosis factor alpha
TEAE	Treatment Emergent Adverse Event
	University College London
UCL	University College London hospital
	Ventilator-Associated Pneumonia
VAP	
WHO	World health organisation

#### **Exploristics Limited**

## Identifier: EXP20012 Clinical Study Identifier: 132333

### 1. INTRODUCTION

The clinical spectrum of SARS-CoV-2 infection (COVID-19) appears to be wide, encompassing asymptomatic infection, mild upper respiratory tract illness (majority of cases) and severe viral pneumonia with respiratory failure and even death in the minority of subjects. In severe viral pneumonia excessive and inappropriate activation of neutrophils can result in the formation of neutrophil extracellular traps (NETs) which exacerbate the clinical course of the pneumonia. These NETs consist of DNA, histones and other components of neutrophils (e.g. myeloperoxidase (MPO)). These NETs are found in the lungs and in the circulation and contribute to organ damage. A treatment that reduces NET formation is likely to reduce the exuberant inflammatory response and thereby improve the clinical course of viral pneumonia and save lives.

NETs have been shown to drive disease in influenza pneumonia as well as in subjects with cystic fibrosis (CF). In addition, their role has been explored in various pre-clinical models of viral infection (mouse and bovine) and shown that reduction of the NETs improves symptoms and increases survival. High neutrophil infiltration is prominent in the lungs of COVID-19 patients and evidence of NET components in the circulation and lung biopsies has been reported in clinical study of COVID-19 patients.

Dornase alfa is a recombinant human DNase I that has been approved since 1994 for the treatment of CF. It is delivered directly to the lungs by nebulisation and has been shown to:

- reduce NETs and inflammation
- reduce the relative risk of developing a respiratory tract infection
- improve pulmonary function in both chronic and acute exacerbation of inflammatory CF

Dornase alfa is safe and well-tolerated in children and adults with CF at doses ranging from 2.5mg QD up to a maximum of 10mg BID.

This study proposes to treat hospitalised subjects with COVID-19 by administration of 2.5mg dornase alfa BID for 7 days. The effect on NETs, inflammation and clinical course will be closely monitored. We expect to see a reduction in circulating NETS and inflammatory biomarkers that will result in clinical benefit. Historic controls will be obtained from an existing database of 120 subjects with COVID-19 that have been admitted to UCL since the beginning of the outbreak.

It is worth noting that dornase alfa can be self-administered at home. Therefore, dornase alfa has the potential to provide benefit in subjects with COVID-19 who have mild disease and are selfisolating and in those discharged from hospital to recuperate at home.

This statistical analysis plan (SAP) describes the key elements of the data handling and analysis strategy that generates evidence of the efficacy and safety of dornase alfa in participants with COVID-19 from the data collected in the study.

### **Exploristics Limited**

## Identifier: EXP20012 Clinical Study Identifier: 132333

### 2. STUDY OBJECTIVE(S) AND ENDPOINT(S)

### 2.1 Study Objective(s)

**Primary objective**: to assess the effect of dornase alfa on C-reactive Protein (CRP) in hospitalised participants with COVID-19.

**Secondary objective**: to assess the effect of dornase alfa on clinical responses in hospitalised participants with COVID-19.

**Exploratory objective**: to assess the effect of dornase alfa on inflammation, biomarkers of NETs, coagulation, complement activation and haemolysis in hospitalised participants with COVID-19.

### 2.2 Study Endpoint(s)

### 2.2.1 Primary Endpoint

The primary endpoint is the levels of acute phase reactant CRP over 7 days follow-up.

#### 2.2.2 Secondary Endpoints

Secondary endpoints include, but are not limited to:

- Levels of acute phase reactant CRP over 35 days follow-up
- Length of hospitalisation from baseline (days)
- Survival at Day35, mortality data collected from EPIC database for both HCs and randomised individuals
- White blood cell count over 7 days follow-up
- Neutrophil count over 7 days follow-up
- Lymphocyte count over 7 days follow-up
- Monocyte count over 7 days follow-up
- Eosinophil count over 7 days follow-up
- Basophil count over 7 days follow-up
- Procalcitonin over 7 days follow-up
- D-dimer count over 7 days follow-up
- Blood pressure over 7 days follow-up
- Pulse rate over 7 days follow-up
- Temperature over 7 days follow-up
- Respiratory rate over 7 days follow-up
- Time on Oxygen over 7 days follow-up
- Time on Oxygen over 35 days follow-up
- Proportion of individuals with Pneumonia over 7 days follow-up
- Ordinal score (WHO scoring tool) over 7 days follow-up (including randomized individuals only)
- Proportion of individuals on Mechanical Ventilation (MV) over 7 days follow-up
- Time on MV over 7 days follow-up
- Length of ICU stay (hours) over 7 days follow-up
- Proportion of individuals with Pneumonia over 35 days follow-up
- Proportion of individuals on Mechanical Ventilation (MV) over 35 days follow-up
- Time on MV over 35 days follow-up
- Length of ICU stay (hours) over 35 days follow-up

### **Exploristics Limited**

## Identifier: EXP20012 Clinical Study Identifier: 132333

### 2.2.3 Exploratory Endpoints

Exploratory endpoints may be measured in the circulation (blood) and, when these are available, in bronchial secretions (spontaneous expectorant or routine bronchoscopy during MV). They may include, but are not limited to:

- Circulating pro-inflammatory cytokines (e.g. IL-6, TNFα, IL-1β, IL-8)
- Cell-free DNA (cfDNA)
- Circulating histone
- Citrullinated H3
- NET Elisa assay
- NET formation assay
- Coagulation (e.g fibrin, tissue factor, Von Willebrand factor, thrombin, thromboxane A2)
- Complement cascade (e.g C1q)
- Haemolysis (e.g RBC lysis)
- Expression profiling of white blood cells by RNA seq

### **2.3 Statistical Hypotheses**

The statistical hypotheses are defined in terms of a 'zero effect' i.e. no difference between the treatments; the null hypothesis. The subsequent analyses test these statements to determine how much evidence there is to support the null hypothesis. A small p-value can be interpreted as a small probability of observing the result we obtained if there really was no difference between treatments, hence leading to rejection of the null hypothesis.

#### 2.3.1 Primary null hypothesis

• There is no difference in CRP levels between hospitalised COVID-19 positive individuals receiving BAC + dornase alfa and hospitalised COVID-19 positive individuals receiving BAC only.

### 2.3.2 Secondary null hypotheses

• There is no difference in secondary endpoints between hospitalised COVID-19 positive individuals receiving BAC + dornase alfa and hospitalised COVID-19 positive individuals receiving BAC only.

### 2.3.3 Exploratory null hypotheses

• There is no difference in exploratory endpoints between hospitalised COVID-19 positive individuals receiving BAC + dornase alfa and hospitalised COVID-19 positive individuals receiving BAC only.

#### **Exploristics Limited**

## Identifier: EXP20012 Clinical Study Identifier: 132333

### 3. STUDY DESIGN

A single-site, randomised, controlled, parallel design, open-label investigation of an approved nebulised recombinant human DNase enzyme (dornase alfa) to reduce hyperinflammation in hospitalised participants with COVID-19 (the COVASE Trial: Figure 1).

#### Figure 1: COVASE Trial Schematic

Participants will be screened, consented, enrolled and randomised up to 3 days after they are admitted to the hospital. They will be randomised in a 3:1 ratio to receive BAC + dornase alfa or BAC alone. A total of 40 participants will be enrolled (30 to receive BAC plus dornase alfa and 10 to receive BAC). On Day1 to Day7 of the trial, participants randomised to the active arm, will receive 2.5mg BID nebulised dornase alfa in addition to BAC. On Day1, Day3, Day5 and Day7, blood samples will be drawn in both trial arms in order to test pharmacodynamic endpoints (PD), biomarkers and clin labs. Clinical assessments will be undertaken daily (as per UCLH clinical guidelines). Participants will be followed until discharge or death or a maximum of 28 days follow-up.

A sample size re-estimation is planned when 12 randomised participants have completed Day7 of follow-up. This analysis will ensure that the assumptions made in the sample size calculation remain valid. However, if the variability is higher than expected then up to an additional 10 participants will be enrolled and treated with dornase alfa (up to 48 participants in total).

CRP has been chosen as the Primary Endpoint because it is a clinically important marker of inflammation and is used to make clinical treatment decisions. In addition, it is induced by the overexuberant inflammation mediated by the NETs and inflammatory histones. CRP is a prognostic marker and correlates with clinical symptoms, inflammation and response to therapy.

Based on clinical judgement, it may be decided to keep some participants on treatment for up to 14 days. In particular, if participants have significant benefits from therapy, but show relapses of the COVID-19 inflammatory state (rising CRP and increasing oxygen requirements in the absence of bacterial infection), on completing 7 days of treatment, then the medical team have the choice of

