Total number of participants planned:	40 participants will be enrolled. A sample size re-estimation is planned to occur approximately one third of the way through the study (e.g. when 12 participants have been randomised). At this point, the decision may be made to randomise additional participants if the variability of the primary endpoint is higher than anticipated.
Main inclusion/exclusion criteria:	Participants who are hospitalised for COVID-19 will be recruited into the study.

Inclusion criteria:

- 1. Male and female participants, aged \geq 18 years.
- Participants who are hospitalised for suspected Coronavirus (SARS-CoV)-2 infection confirmed by polymerase chain reaction (PCR) test or radiological confirmation with chest CT scan
- Participants with stable oxygen saturation (>=94%) on supplementary oxygen
- 4. CRP >= 30 mg/L.
- Participants will have given their written informed consent to participate in the study and are able to comply with instructions and nebuliser.

Exclusion criteria

- Females who are pregnant, planning pregnancy or breastfeeding.
- Concurrent and/or recent involvement in other research or use of another experimental investigational medicinal product that is likely to interfere with the study medication within the last 3 months before study enrolment.
- 3. Serious condition meeting one of the following:
 - respiratory distress with respiratory rate >=40 breaths/min
 - II. oxygen saturation <=93% on high-flow oxygen
- 4. Require mechanical invasive or non-invasive ventilation at screening
- Concurrent severe respiratory disease such as asthma, COPD and/or ILD.
- Any major disorder that in the opinion of the Investigator would interfere with the evaluation of the results or constitute a health risk for the study participant.
- Terminal disease and life expectancy <12 months without COVID-19.
- 8. Known allergies to the dornase alfa and excipients.
- 9. Participants who are unable to inhale or exhale orally throughout the entire nebulisation period.

Statistical methodologyFull details of the planned statistical analysis will be presented in
the Statistical Analysis Plan (SAP). All baseline data,
demographics, endpoints, safety and tolerability will be
summarised overall and by treatment group and by day. In
general, continuous data will be summarised using the mean
(standard deviation), median (1st and 3rd quartiles), minimum

and maximum, and categorical data will be represented as frequency counts (percentages).

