5.1 Overall design

A single-site, randomised, controlled, parallel design, open-label investigation of an approved nebulised recombinant human DNase enzyme (dornase alfa) to reduce hyperinflammation in hospitalised participants with COVID-19 (the COVASE Trial: Figure 2).

Figure 2: COVASE Trial Schematic

Participants will be screened, consented, enrolled and randomised up to 3 days after they are admitted to the hospital. They will be randomised in a 3:1 ratio to receive BAC + dornase alfa or

BAC alone. A total of 40 participants will be enrolled (30 to receive BAC plus dornase alfa and 10 to receive BAC). On Day1 to Day7 of the trial, participants randomised to the active arm, will receive 2.5mg BID nebulised dornase alfa in addition to BAC. On Day1, Day3, Day5 and Day7, blood samples will be drawn in both trial arms in order to test pharmacodynamic endpoints (PD), biomarkers and clin labs. Clinical assessments will be undertaken daily (as per UCLH clinical guidelines). Participants will be followed until discharge or death or a maximum of 28 days follow-up.

A sample size re-estimation is planned when 12 participants have been randomised. This analysis will ensure that the assumptions made in the sample size calculation remain valid. However, if the variability is higher than expected then up to an additional 10 participants will be enrolled and treated with dornase alfa (up to 50 participants in total).

CRP has been chosen as the Primary Endpoint because it is a clinically important marker of inflammation and is used to make clinical treatment decisions. In addition, it is induced by the over-exuberant inflammation mediated by the NETs and inflammatory histones. CRP is a prognostic marker and correlates with clinical symptoms and response to therapy. Thus, CRP is at the centre of the COVID-19 disease pathway: from NETS to CRP to clinical disease progression.

Based on clinical judgement, it may be decided to keep some participants on treatment for up to 14 days. In particular, if participants have significant benefits from therapy, but show relapses of the COVID-19 inflammatory state (rising CRP and increasing oxygen requirements in the absence of bacterial infection), on completing 7 days of treatment, then the medical team have the choice of reinstating dornase alfa treatment for up to 7 further days (14 days in total). Blood sampling, as specified, will continue until the last day of dosing with dornase alfa.

Study controls

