6.5 Concomitant medication

Participants in the COVASE trial will continue to receive best available care (BAC) per UCLH guidelines. Dornase alfa will be administered in addition to BAC.

BAC currently consists of symptomatic relief: antipyretics, analgesics and intravenous fluids if needed. In addition, patients may need supplemental oxygen and/or mechanical ventilation.

There is no basis to support a drug-drug interaction risk, as this is a recombinant human protein that is administered directly to the lungs. Systemic exposure is very low and dornase alfa is cleared by proteinases present in the lungs.

There is a potential risk that other medications administered as BAC may affect the endpoints in the study e.g. decrease CRP. However, this cannot be avoided and will be considered in the analysis plan for the data. Furthermore, a sample-size re-estimation is planned in order to take this potential source of unexpected variability into account.

Concomitant medications will be recorded in the participant's medical records/CRF.

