11.4 Interim analysis

An interim analysis will be conducted when 12 participants have been randomised. The results of the interim analysis will be used to re-estimate the sample size if necessary. The interim analysis will be conducted by an independent statistician in a secure, password protected environment. The analysis will involve the production of descriptive statistics for the primary endpoint, AEs and baseline characteristics by study population and by treatment. No formal statistical comparison between the treatment groups will be performed. The sample size re-estimation may result in the recruitment of more subjects than originally planned but not less.

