### 4. PLANNED ANALYSES

There are two planned analyses, an interim analysis after 12 randomised individuals have completed Day7 follow-up and the final analysis, once all randomised individuals have completed follow-up (which is the minimum of discharge, death or 35 days after randomisation). At the interim analysis, only the primary endpoint and safety data will be examined, and no secondary or exploratory endpoints. A promising zones approach [1] (see Section 12 for details) will be followed at the interim analysis stage to identify the conditional power and make a decision as to whether to continue enrolment up to the planned 40 individuals randomised, or whether to increase the planned sample size up to a maximum of 48 randomised individuals. See Section 12 for details.

After the final randomised participant has completed follow-up, a more complete analysis will be undertaken, including examination of endpoints relating to the primary, secondary and exploratory objectives. A full safety analysis will also be carried out at this stage.

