#### 8.3 Examination of Subgroups

#### 8.3.1 Primary endpoint analyses

At the interim and final analyses, the primary analysis will be to combine the two sets of individuals on BAC only in the comparator population to the individuals randomised to BAC + dornase alfa.

However, three additional analyses will be carried out at the final analysis for the primary endpoint analysis.

- 1. A comparison of the BAC + dornase alfa arm to those randomised to BAC only (no historical controls)
- 2. A comparison of the BAC + dornase alfa arm to matched historical controls (no individuals randomised to BAC only)
- 3. A comparison of those randomised to BAC only to matched historical controls (within control comparison).

The treatment effect estimate will be compared between the primary analysis and analyses 1. and 2. above. No formal test will be carried out to test the difference in treatment effect between the three analyses, but substantial differences will be noted.

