#### **Exploristics Limited**

## Identifier: EXP20012 Clinical Study Identifier: 132333

- 10 individuals randomised to BAC only
- 60 individuals (2 × the number of individuals randomised to BAC + dornase alfa) included from the matched historical control cohorts

Therefore the planned sample size is 100 individuals.

However, at the interim analysis, a sample size re-estimation will be carried out, and the overall sample size could be increased to a maximum of:

- 36 individuals randomised to BAC + dornase alfa
- 12 individuals randomised to BAC only
- 72 individuals (2 × the number of individuals randomised to BAC + dornase alfa) included from the matched historical control cohorts

Giving a maximum permitted sample size of 120 individuals.

A decision rule for whether to increase the number of individuals randomised into the trial will be derived using a promising zones approach [1]. This approach calculates the power at the interim analysis, conditional on the interim standardised treatment effect size, termed the conditional power. The conditional power at the interim stage will fall into one of three possible zones, a futility zone, a promising zone or a favourable zone.

- If the conditional power is below 0.46 it will be considered to fall into the futility zone. If the conditional power is in the futility zone at the interim analysis, it is unlikely that the final analysis will produce a p-value of <0.05 for the treatment effect, even if the sample size were increased to the maximum permitted sample size of 48 individuals randomised. Therefore, if the conditional power falls in the futility zone at the interim, recruitment will continue as planned to 40 randomised individuals and a final analysis will be performed as originally planned.

- If the conditional power is between 0.46 and 0.8, it will be considered to fall into the promising zone. In this zone, there is less than the 80% power that the study was powered for originally, but if the sample size were to be increased to somewhere between 40 and 48 randomised individuals, the power could be increased to close to 80%, and there would be an increased probability of observing a p-value of <0.05 for the treatment effect at the final analysis.

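### The sample-size re-estimation has two different triggers and two different sets of added patients in current text, and the power described for the promising zone is not reached in its lower part

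*SAP*

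**What the plan says.** **Rule based on variability.** The Protocol summary (section 2) allows additional participants to be randomised "if the variability of the primary endpoint is higher than anticipated". Protocol 5.1 says that if "variability is higher than expected then up to an additional 10 participants will be enrolled and treated with dornase alfa (up to 50 participants". SAP section 3 repeats this with a different total: "variability is higher than expected then up to an additional 10 participants will be enrolled and treated with dornase alfa (up to 48 participants".

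**Rule based on conditional power.** SAP section 4 says the interim will "identify the conditional power and make a decision as to whether to continue enrolment up to the planned 40 individuals randomised" or to enlarge to at most 48. SAP section 12 defines the quantity: "This approach calculates the power at the interim analysis, conditional on the interim standardised treatment effect size, termed the conditional power". Between 0.46 and 0.80 is the promising zone, where the number randomised may rise. Below or above it, 40 are randomised. The stated maximum is 36 on dornase alfa, 12 on BAC and 72 matched historical controls. In the promising zone, SAP section 12 says that a size between 40 and 48 could bring power near 80%.

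**What the interim may contain.** Protocol 11.4 provides for descriptive statistics by treatment and states: "No formal statistical comparison between the treatment groups will be performed". SAP 8.3.1 says: "At the interim and final analyses, the primary analysis will be to combine the two sets of individuals on BAC only" and compare them with the dornase alfa arm. SAP section 12 lists the primary endpoint analysis among the interim analyses.

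**Timing.** Protocol 11.2.1 and 11.4 place the interim when 12 participants have been randomised. SAP sections 3, 4, 5 and 12 place it when 12 have completed Day7.

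**The concern.** A sample-size rule that depends on interim data has to be fixed in advance and read only one way. Here two rules stand side by side in the current SAP, so it does not help to say that the SAP supersedes the protocol. One rule looks at the spread of CRP and the other at the observed treatment effect. The trial team could follow either, reach different decisions on the same data, and cite current text each time. They would also recruit different patients: up to 10 on dornase alfa only, or 8 randomised 3:1.

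The power sentence matters for a separate reason. Whoever acts on the interim result needs to know what enlargement can buy. The cap allows a 1.2-fold increase, which looks small against a conditional power that may start as low as 0.46.

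**Working it through.** **1. The passages side by side**

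| | Trigger | Added patients | Cap stated | Sum |
|---|---|---|---|---|
| Protocol 5.1 | high variability | up to 10, all dornase alfa | 50 | 40 + 10 = 50 |
| SAP section 3 | high variability | up to 10, all dornase alfa | 48 | 40 + 10 = 50, not 48 |
| SAP section 12 | conditional power 0.46 to 0.80 | 36 − 30 = 6 dornase alfa, 12 − 10 = 2 BAC | 48 | 36 + 12 = 48 |

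**2. Inputs for conditional power**

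- Two-sided 5% test, critical value 1.96 (SAP 11.1).
- Interim size n1 = 30: 9 dornase alfa, 3 BAC, 18 historical (SAP section 12).
- Planned size n2 = 100 and maximum 120 (SAP section 12), corresponding to 40 and 48 randomised.
- Information for a two-group comparison, nA × nC / (nA + nC): 9 v 21 gives 6.3; 30 v 70 gives 21; 36 v 84 gives 25.2. The ratios 6.3/21 = 0.30 and 25.2/21 = 1.2 match 30/100 and 120/100, so totals can be used directly.

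Conditional power under the observed trend, for final size n:

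CP(n) = Φ( z1·√(n − n1)/√n1 − (1.96·√n − z1·√n1)/√(n − n1) )

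**3. The plan's own 0.46**

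The critical value that preserves the type I error at the enlarged size is

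b = [ √((120 − 30)/(100 − 30)) · (1.96·√100 − z1·√30) + z1·√30 ] / √120.

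Setting b = 1.96 gives z1 = 1.0276 and CP(100) = 0.460. The SAP's lower limit of 0.46 reproduces.

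**4. Power at the cap**

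At the lower limit, z1 = 1.0275:

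- CP(100) = Φ(1.5696 − 1.6700) = Φ(−0.100) = 0.46
- CP(120) = Φ(1.7797 − 1.6700) = Φ(0.110) = 0.54

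| Conditional power at 40 randomised | z1 | At 48 randomised |
|---|---|---|
| 0.46 | 1.028 | 0.54 |
| 0.50 | 1.074 | 0.59 |
| 0.60 | 1.190 | 0.69 |
| 0.70 | 1.314 | 0.78 |
| 0.80 | 1.459 | 0.87 |

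Solving CP(120) = 0.75 gives a starting value of about 0.67. Solving CP(120) = 0.80 gives about 0.72. From 0.46, reaching 0.80 would need a total of about 213, against the maximum of 120.

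**5. Can the two triggers disagree?**

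For an unadjusted, untransformed comparison of 9 v 21, z1 = (difference/SD)·√6.3, so difference = z1·SD/√6.3. With the SD exactly at the design value of 62 mg/L:

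- lower limit of the zone: 1.0275 × 62/2.510 = 25.4 mg/L
- upper limit of the zone: 1.4592 × 62/2.510 = 36.0 mg/L

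For an interim difference of about 25 to 36 mg/L, SAP section 12 adds patients. The variability rule does not, because variability is as expected.

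**The case against.** **The two rules overlap.** The effect in SAP section 12 is standardised, so a larger SD lowers conditional power. The Protocol wording is also permissive: it sets no threshold for high variability and says only that up to 10 may be added. Disagreement in the opposite direction is therefore soft. With the difference at design (0.40 × 99 = 39.6 mg/L) and an SD from 62 to about 68, section 12 adds none, but adding none would not breach Protocol 5.1. This stands. It does not remove the case in step 5, where only one rule adds patients, nor the conflict over who is added.

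**Protocol 11.4.** A reader might infer that it forbids calculating conditional power at all. That goes too far: it provides for by-treatment summaries of the primary endpoint and uses the results for re-estimation, and an unadjusted conditional power can be obtained from means and SDs. The clear conflict is with the between-group primary analysis that SAP 8.3.1 and section 12 run at the interim.

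**Protocol 6.5.** The statement that "a sample-size re-estimation is planned in order to take this potential source of unexpected variability into account" might be read as another trigger. It gives a reason for the re-estimation, not a rule for adding patients.

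**The power wording.** SAP section 12 says power could be raised and does not define how near to 80% is near enough. A single cut-off cannot be attributed to the SAP: about 0.67 applies if 75% is near enough, about 0.72 if 80% is required. On either reading the sentence fails in the lower part of the zone.

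**The futility sentence.** Just below 0.46, conditional power at 48 would still be about 0.54, so a reader might call that sentence wrong too. Only the boundary is affected. In simulated interims under the design assumptions (difference 39.6, SD 62, 9 v 21), mean conditional power at 48 across the futility zone is about 0.19, so the SAP's description of the zone is fair.

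**Type I error.** A reader might also infer inflation from the effect-based rule. Step 3 shows that the 0.46 limit is where the conventional test remains valid for this cap, so none is alleged.

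**Timing.** The SAP largely makes the protocol's statement more specific. This is a lesser point.

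**Conclusion.** Wrong as written. The contradiction in trigger, allocation and cap rests on the text alone and needs no model: variability with up to 10 on dornase alfa (50 in the Protocol, 48 in SAP section 3, although 40 + 10 = 50), against conditional power of 0.46 to 0.80 with 6 + 2. The interim between-group analysis in the SAP is not reconciled with Protocol 11.4.

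The power sentence is correct only in the upper part of the promising zone. At the cap of 48, conditional power is 0.54 at the lower limit and reaches 0.80 only from about 0.72. These figures assume the SAP's own sizes (30, 100, 120), two historical controls per dornase alfa patient, independent increments and the conventional final test.

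The 25 to 36 mg/L example is illustrative, because SAP 11.1 plans an adjusted repeated-measures model with possible transformation.

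**What to change.** State one trigger, one cap, one allocation and one interim time in both documents, and align Protocol sections 2, 5.1, 11.2.1 and 11.4 with SAP sections 3, 4, 5 and 12.

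If SAP section 12 is the intended rule:

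- Protocol 5.1 and SAP section 3: *When 12 randomised participants have completed Day7, conditional power is calculated. If it is at least 0.46 and below 0.80, up to 8 more participants are randomised 3:1 (6 dornase alfa, 2 BAC; 48 in total). Otherwise 40 are randomised.*
- SAP section 12: state how the number up to 48 is chosen, for example 48 throughout the zone.
- Protocol 11.4: permit the interim primary analysis and the conditional power calculation.
- SAP section 12, in place of the power sentence: *At 48 randomised, conditional power is 0.54 if the interim value is 0.46, 0.69 if 0.60, 0.78 if 0.70, and reaches 0.80 only from about 0.72.*

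The cost is text changes plus a protocol amendment approved before it is implemented (Protocol section 15). The stated power becomes less favourable. If the interim decision has already been taken, report the trigger, number and allocation actually used as a justified deviation under Protocol 11.5.
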